**a) Screening visit and Run-in Period (YNHH Hospital Research Unit):**

[figure not shown]
At the screening visit, study subjects will complete the informed consent form for participation in voluntary clinical research. Demographic and clinical data collected will be reviewed by study personnel to confirm eligibility.

Once consented, all subjects will be further screened with a medical history and physical examination, blood work (electrolytes, hematocrit, creatinine, liver function tests and HbA1c) and a 12-lead electrocardiogram (EKG). In subjects who do not already take advantage of continuous glucose monitor (CGM) systems, a CGM (iPRO monitor, Medtronic) will be applied and keep in position for 7 days. After 7 days, glucose CGM data will be downloaded to determine degree and frequency of hypoglycemia during a brief visit. In subjects already using a CGM system, glucose data will be downloaded and analyzed by study staff to determine degree and frequency of hypoglycemia. The subject will perform a preliminary cognitive test (Montreal Cognitive Assessment) and a questionnaire to evaluate hypoglycemia unawareness, see Appendix 3).

If the subject is eligible for the study, the subsequent sessions to complete the study will be scheduled. The subject will be asked to record CGM data in the 4 weeks before the first study session (run-in period) to collect baseline data on glucose control. In the event that scheduling issues preclude the sequencing of scanning sessions as described below, certain modifications can be made to accommodate a subject. In particular, the duration of the intervention may vary from 8 to 10 weeks and the cognitive assessments may be scheduled up to 1 week before the corresponding MRS session.

**b) MRS studies and hyperinsulinemic hypoglycemic clamps (Magnetic Resonance Research Center)**

Subjects will be asked to remain fasting from midnight prior to the study and to check their blood glucose at home before bed and on awakening to ensure that the glucose level is above 70mg/dl and below 200mg/dl. They will be

**Figure 5: Overall Study Design.** A) Following a 1 week of CGM screening for hypoglycemia, eligible T1DM patients will undergo 4 weeks of CGM for run-in and then will be randomized to 8-10-week therapy with PLGS insulin pump in either auto or manual mode. B) MRS study with timeline for hyperinsulinemic-hypoglycemic clamp and carbon-13 tracer infusion.

instructed to call [name] with any readings outside of this range. Upon arrival to the MRRC (7:30AM), their blood glucose will be checked as a safeguard, and insulin received via the insulin pump will be held. An IV catheter will be inserted for infusion of insulin and glucose to maintain normal glucose levels. A urine pregnancy test will be completed on all female subjects of child bearing potential. Any female testing positive will be excluded from the study. A second IV catheter will be inserted for arterialized venous blood sampling and then patients will be placed in the scanner for MRS. MRS measurement will be performed under clamped insulin-induced hypoglycemia as described below. At the end of the clamp procedure, a symptom questionnaire will be administered, asking the subjects to rate the intensity of their symptoms on a scale from 0 to 7 (none to severe) [13] (Appendix 4). Neuroglycopenic (dizziness, tingling, blurred vision, difficulty in thinking, faintness) and autonomic symptoms (anxiety, palpitations, hunger, sweating, irritability, or tremor) are included in this assessment, which has been well validated over time. The visit will last no longer than 4 hours, including ~130 minutes of hypoglycemic clamp and MR spectroscopy.

After 8 weeks, both groups will undergo repeat MRS assessment of brain metabolism study according to the same procedures. They will then resume their previous out-patient care via insulin pump.

*Hypoglycemic Clamp:* To produce a controlled hypoglycemic state with a target glucose level of 55mg/dl, we will use the hyperinsulinemic-hypoglycemic clamp method that gently lowers plasma glucose levels according to the protocol that was developed at Yale and is broadly used for these types of studies [29, 27, 28]. All subjects will receive a continuous insulin infusion (2mU/kg/min) and a variable infusion of 20% dextrose (see Fig.6B), which is titrated based on plasma YSI glucose measurements sampled every 5 minutes from a second IV line placed in the opposite arm. During the clamp procedure the plasma glucose level will be gently lowered from the initial level of 95-100mg/dl to the target of  $50 \pm 3$  mg/dL.

Throughout, blood is obtained for glucose, ketones, lactate, insulin, glucagon, cortisol, and catecholamines and will be assayed using established RIA, HPLC & ELISA methods in the YCCI Core Lab (see blood draw schedule below).

	start hypo clamp	glucose ~55mg/dl for ~10-15min	glucose ~55mg/dl for ~20-25min							
Timeline	-60 min	-10 min	 C-tracer Baseline start infusion*	+5	+10	+15	+30	+60	+90	+120
Insulin	X		X			X	X	X		X
Ketones	X		X			X	X	X		X
Lactate	X		X			X	X	X	X	X
C  enrichment			X	X	X	X	X	X	X	X
Counterreg. hormones	X	X	X				X	X		X
Glucose	-----glucose every 5 min during hypo clamp-----									

\* blood draws timed to labeled acetate infusion

Counter-regulatory hormones = epinephrine, norepinephrine, glucagon, cortisol, growth hormone

At the end of the study, insulin will be stopped and the 20% dextrose infusion increased to restore normoglycemia. Subjects will eat and IV cannulas will be removed. Once each subject is clinically recovered with stable blood glucose levels above 80 mg/dL, they can be discharged.

*Magnetic Resonance Spectroscopy:* During the MRS studies, subjects will lie supine in a 4T 94 cm bore magnet. After head positioning under the coil, anatomical images will be obtained for localization of a circa 30ml voxel within the frontal cortex. Following power calibrations, non-iterative shimming and achievement of stable hypoglycemia all study subjects will receive a bolus of [2-13C]acetate (Isotech, Williamsburg, OH) 6 mg/kg · min administered for 5 minutes followed by a continuous infusion of 3 mg/kg · min for a total of 120 minutes, according to our previously published protocol [11, 66]. Then localized 1H-[13C]-MRS measurements with a temporal resolution of 5 min/ spectrum will be performed and selective POCE data acquired to the steady state label concentrations and fractional enrichments of acetate, and the C4 positions of glutamate and glutamine.

**c) Cognitive, symptom and quality of life assessment (YNHH Hospital Research Unit/MRRC/ Long Wharf Diabetes Research Suite (#503) at [name]):**

On a day close to each MRS study, subjects will arrive at the Long Wharf Diabetes Research Suite to perform a baseline assessment of cognitive performance. CGM data will be obtained. A battery of validated cognitive tests that were shown to be associated with severe hypoglycemia in older adults with T1DM will be completed, including Symbol Digit Modalities, Trail Making Test, Grooved Pegboard Test [77]. In addition, we will use validated questionnaires to determine the degree of hypoglycemia unawareness, quality of life and satisfaction of insulin therapy [78-80] (see Appendix 4).

**d) Randomization and follow-up visits between MRS assessments (YNHH Hospital Research Unit/MRRC/Long Wharf Diabetes Research Suite (#503) at [name]):**

After completion of the first MRS session, subjects will randomized to either the intervention or control group. The intervention group consists of treatment with a PLGS-enabled insulin pump/CGM combination (Medtronic MiniMed 670G pump with Guardian sensor, or Tandem t:slim X2 pump with Dexcom sensor) in auto mode for Medtronic users and with Basal-IQ for Tandem users; subjects in the control group will use the same PLGS-enabled insulin pump/CGM combination but in manual mode for Medtronic users or without Basal-IQ for Tandem users. All subjects will undergo a PLGS system training session with a study nurse or nurse practitioner. Subjects will have weekly phone calls with study team members (physician and/or advanced practice nurse or registered nurse) to review blood glucose logs and insulin doses, potential adverse events, and other clinical or device-related issues. Subjects can also speak with a study physician, advanced practice nurse or registered nurse more frequently if there are any questions or concerns.

The two pump devices that will be used are: Medtronic MiniMed™ 670G system or Tandem t:slim X2 with Control IQ software. For subjects who use multiple daily injections as part of their standard insulin therapy or for subjects who do not use the MiniMed 670G pump or t:slim X2 pump, a loaner MiniMed 670G system will be provided. For subjects who use multiple daily injections as part of their standard insulin therapy, the training and support described above will be provided and may potentially be provided on a more frequent and/or intensive basis depending on the needs of the subject. A washout is not required given that regardless of method of administration (pump or injection), the insulin and dosages remain the same. Likewise, the risks remain similar. Furthermore, regardless

of the method of administration that the subject uses in their usual standard of care, all subjects will be trained and supported as much as is necessary in order to ensure that they understand how to use the PLGS system, and any subject who, in the opinion of the clinical study staff, is deemed to not be able to safely use the system will not continue in the study.

Program on Aging field core staff will remain in close contact with study participants via phone to identify and eliminate any obstacles to successful study completion.

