The current “state-of-the-art” treatment for T1DM in the US is sensor-augmented insulin pump therapy. Large-scale studies have demonstrated the benefit of these devices on HbA1c and a reduction in hypoglycemia [62-65]. Despite these improvements, human control of sensor-augmented pump therapy requires frequent, almost nearly continuous, surveillance of the system, and despite the use of audible alarms to warn of actual or impending hypoglycemia, sensors alone do not eliminate the risk of hypoglycemia. The true power of continuous glucose sensors can be better exploited in a “closed-loop” system in which sensor-detected glucose levels dynamically inform and adjust insulin delivery commands through the pump and even suspend basal insulin infusion in the setting of hypoglycemia. This so-called “low-glucose suspend” feature would by design limit hypoglycemia duration and/or magnitude. Due to the greater risk of severe hypoglycemia with seizures at night [66-69], and since most patients don’t respond to alarms when asleep [70], such automatic “threshold suspend” pumps, now approved by the FDA and widely available for T1DM patients, have been very effective in reducing the magnitude and duration of hypoglycemia by up to 30% [71, 72]. However, while these results are encouraging, they were not specifically tested in more vulnerable older adults with T1DM. In addition, the degree to which PLGS technology can reverse brain metabolic adaptations to hypoglycemia has not been determined. This study will, for the first time, define the effect of PLGS systems on reducing the impact of hypoglycemia on brain metabolism and function in older T1DM patients.

g. Special considerations regarding older adults with T1DM.

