Auto Mode: The MiniMed 670G Insulin Pump is capable of continuous insulin delivery, at set and variable rates, for the management of diabetes mellitus in persons requiring insulin. When used with the CGM components (Guardian 3 sensor and transmitter), the pump system is capable of continuous or periodic monitoring of glucose levels in the interstitial fluid under the skin and detection of possible low or high blood glucose episodes. The pump also displays continuous glucose values, storing this data so that it can be retrospectively analyzed to track patterns and improve diabetes management. These features are similar to the commercially available Medtronic sensor-enabled system. The MiniMed 670G Insulin Pump also includes the closed loop algorithm and SmartGuard feature that may be enabled by the user. The SmartGuard feature enables insulin to suspend before a sensor glucose threshold is reached. The closed loop and SmartGuard feature will not be active at the same time. When closed loop is enabled on the MiniMed 670G insulin pump, the sensor glucose values received from the transmitter by the insulin pump will be used to automatically calculate the insulin dose. It will then deliver insulin to the patient, at five minute intervals, to achieve glycemic control. This is in addition to user-defined insulin boluses that patients will continue to require for meals. When Closed Loop is not enabled, the user may have the SmartGuard feature enabled. Here it will suspend basal rate delivery before the sensor glucose value has reached the programmed low threshold.

Manual Mode: If neither the Closed-Loop nor the SmartGuard features are enabled, the pump will deliver pre-programmed basal rates without modulation by the sensor. In this way, manual mode functions like any other insulin pump system. That is, there is no change in the level of technology when compared to the subject's existing insulin pump. The only exception to this is if the SmartGuard feature is enabled, which will be determined by experienced study clinicians.

Basal-IQ: The Basal-IQ feature helps reduce the frequency and duration of low-glucose events by predicting glucose levels 30 minutes ahead and suspending insulin if the patient is expected to drop below 80 mg/dL or if glucose is currently below 70 mg/dl and falling. The system resumes basal insulin delivery once glucose values start to rise.

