- All Co-Investigators listed on the protocol.
- Yale Center for Clinical Investigation Research Subject Advocates (RSAs)

The principal investigator [name] will conduct a review of all adverse events upon completion of every study subject. The principal investigator will evaluate the frequency and severity of the adverse events and determine if modifications to the protocol or consent form are required.

- d. For multi-site studies for which the Yale PI serves as the lead investigator:
  - i. How will adverse events and unanticipated problems involving risks to subjects or others be reported, reviewed and managed?
  - ii. What provisions are in place for management of interim results?
  - iii. What will the multi-site process be for protocol modifications?  
N/A

**10 Statistical Considerations:** Describe the statistical analyses that support the study design.

To test the hypothesis that “*Strict avoidance of hypoglycemia for 8 weeks reduces frontal cortex C-acetate utilization by 25%*” a two-sided nonparametric Wilcoxon rank sum test will be used. SAS® statistical software, version 9.4, will be used to conduct data analyses.

Sample size estimation and power calculation have been conducted with PASS statistical software. [86, 87]. Sample size estimates are based on published human acetate data, as well as our previously published differences between control and RH animal studies [48, 56]. These differences correspond to a decrease of approximately 25% or more in brain acetate utilization in the group of T1DM patients undergoing the PLGS intervention. We estimate that sample sizes of 12 subjects per group will achieve 80% power to detect this 25% reduction with estimated group standard deviations of 0.18 and 0.10 in the respective control and intervention groups, using a two-sided Wilcoxon rank sum test and assuming a significance (alpha) level of 0.05. To adjust the sample size for possible missing values, three additional study participants will be enrolled per treatment group; we thereby estimate that a sample size of 15 per group will be adequate to test the proposed primary hypothesis.

SECTION II: RESEARCH INVOLVING DRUGS, BIOLOGICS, RADIOTRACERS, PLACEBOS AND DEVICES
--

*If this section (or one of its parts, A or B) is not applicable, state N/A and delete the rest of the section.*

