## GENERAL WARNINGS

- Do not use the pump when a flammable anesthetic mixture with air, oxygen, or nitrous oxide is present. These environmental conditions can damage your pump and result in serious injury.
- Always use the fingertip for blood samples used for calibrating the sensor while in Auto Mode. The fingertip was the only site studied for use with Auto Mode. Do not use blood samples from the palm to calibrate the sensor as this site was not studied for use with Auto Mode and the performance of the system is not known.
- Do not make treatment decisions, such as determining your insulin dose for meals, using the MiniMed™ 670G continuous glucose monitor (CGM) values, as they are not intended to be used to make such treatment decisions. The MiniMed™ 670G CGM does not replace a blood glucose meter. Always use the values from your blood glucose meter for treatment decisions. Blood glucose values may differ from sensor glucose values. Using the sensor glucose readings for treatment decisions could lead to high or low blood glucose.
- Never rely on the pump beeps or vibrations alone to navigate through the pump screens or menus. Always check your pump screen as you navigate. The pump beeps and vibrations are intended to notify you of a condition that may require attention. Relying on the pump beeps or vibrations alone to navigate can result in incorrect menu selection or settings.
- Do not use your pump if the screen appears broken or unreadable. In some instances, impact to the pump can damage the screen while the buttons continue to function. If the screen is broken or unreadable, do not press any buttons. Remove the pump and begin using your backup insulin plan per the direction of your healthcare professional. If the pump is accidentally programmed while the screen is broken or unreadable, this could result in high or low blood glucose levels. If your screen is damaged, contact the 24-Hour Technical Support to arrange for shipment of a replacement pump.
- Only use rapid acting U100 insulin (Humalog® and Novolog®) that has been prescribed by your healthcare professional for use with an infusion pump. Do not put any other drugs or medications inside your reservoir for use with this pump. Other drugs or medications are not intended for use with this pump. Use of other drugs or medications can cause serious injury.

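### Entry therapy is mixed and is neither stratified nor adjusted for, so control assignment is a different change for different participants, and chance imbalance with 15 per arm is not rare.

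*Combined protocol and SAP*

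**What the plan says.** **Who enters.** Section I, 3.d admits people on multiple daily injections and people on any pump. On equipment it says: "for subjects who do not use the MiniMed 670G pump or t:slim X2 pump, a loaner MiniMed 670G system will be provided". The only loaner is a 670G, so every Tandem participant must already own a t:slim X2. The inclusion and exclusion criteria (Section I, 7) do not mention prior pump, sensor or suspend use. The background (Section I, 2.f) calls threshold-suspend pumps "now approved by the FDA and widely available for T1DM patients".

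**What is assigned.** After the first scan, participants are randomised to the study pump and sensor with the automated feature on (intervention) or off (control). Appendix 6 tells candidates that either group is equally likely. No stratification, blocking or minimisation is described.

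**What control is said to be.** The Manual Mode paragraph of the Research Plan says "there is no change in the level of technology when compared to the subject's existing insulin pump". It then lets study clinicians enable SmartGuard. Section I, 3.d waives a washout because "regardless of method of administration (pump or injection), the insulin and dosages remain the same", and adds that the risks are similar.

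**Analysis.** The Statistical Considerations plan an unadjusted rank-sum comparison and claim that "sample sizes of 12 subjects per group will achieve 80% power to detect this 25% reduction", "using a two-sided Wilcoxon rank sum test and assuming a significance (alpha) level of 0.05". Three more are enrolled per group for missing values, giving 15.

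**The concern.** The stated aim is to see whether PLGS, through strict avoidance of hypoglycemia, reverses an existing brain adaptation. That is a clean question for a pump user without automated suspend. For an owner who already runs the feature, the baseline scan is taken on treatment: intervention means no change and control means withdrawal. For an injection user, control brings a new pump, and a sensor if none was used before. Control assignment is thus not one condition relative to baseline.

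Two things are at stake. With 15 per arm and no stratification, one arm can by chance hold noticeably more of one entry therapy, and the unadjusted test does nothing about it. The effect may also differ by entry therapy, and if pump mode at entry is not recorded, a null or surprising result could not be traced to that.

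**Working it through.** **1. The plan's own figure.** Inputs from the Statistical Considerations: two-sided rank-sum test, alpha 0.05, SDs 0.18 (control) and 0.10 (intervention), 12 per group, 80% power, 25% reduction. The control mean is not given, so the absolute difference is unknown.
- Root-mean-square SD = √((0.18² + 0.10²)/2) = 0.1456.
- Simulated rank-sum power with 12 per group is about 80% at a difference of 0.185, which implies a control mean of 0.185/0.25 = 0.74.
- Simulated power at control means of 0.6, 0.7, 0.8 and 1.0 is about 63%, 75%, 86% and 96%.
- Allowance for missing values: 12/(1 − 0.20) = 15, as stated.

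The 12 per group is consistent with a control mean near 0.74 but cannot be confirmed.

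**2. Chance imbalance.** Assume 15/15 allocation without stratification, and that K of the 30 share one entry therapy. The number x in one arm is hypergeometric: P(x) = C(15, x)·C(15, K − x)/C(30, K). The arms differ by |2x − K|. K is not in the documents, so a range is shown.

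| K of 30 (assumed) | P(arms differ by 4 or more) |
|---|---|
| 6 | 2 × (5,005 + 45,045)/593,775 = 17% |
| 8 | 2 × (6,435 + 96,525 + 525,525)/5,852,925 = 21% |
| 10 | 2 × (3,003 + 75,075 + 675,675 + 2,927,925)/30,045,015 = 25% |

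For K = 6, a difference of 4 is a 5-to-1 split.

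**3. What control changes, by entry therapy.**

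| At entry | Assigned on | Assigned off |
|---|---|---|
| Injections | gains pump, sensor if new, and feature | gains pump, and sensor if new |
| Pump, feature not in use | gains feature | little change in insulin delivery |
| Study pump, feature in use (permitted, not stated) | no change | loses feature |

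Within every row the arms still differ by feature on against feature off. That holds whether the analysed value is the follow-up scan or the change from baseline.

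**4. Worst-case illustration only.** Suppose the control mean is 0.74, and k of 12 intervention participants follow the control distribution exactly, so that the feature does nothing for them. Power falls from about 80% to 61–62% (k = 2) or 50–51% (k = 3). If they keep half the effect, it is about 72% or 67%. If they respond like the others, it stays at 80%. With zero effect and k = 3, control means from 0.6 to 1.0 give 37% to 74%. Neither k nor the loss of effect has a source in the documents.

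**5. Text side by side.**
- *Injection users.* Section I, 3.d says insulin, dosages and risks carry over. The device warnings (Section II, C) say "Only use rapid acting U100 insulin" and state that the safety of Auto Mode and the suspend functions in people without pump experience is not known.
- *Control participants.* The Manual Mode sentence compares only with an existing pump, so it fails for anyone whose feature is switched off and says nothing about injection users. The same paragraph allows SmartGuard in manual mode. Appendix 6 describes the alternative to the new pump as continuing standard pump therapy, while Section I, 3.d puts everyone on a study pump.

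**The case against.** The strongest reply is that nothing is diluted. A reader might infer that prior suspend users are in the trial and that the planned contrast is therefore weakened by a known amount. The documents support neither step. They permit owners of the study pumps to enrol but never say that any has Auto Mode or Basal-IQ on. The feature is assigned on or off within every entry therapy, and both arms receive the study pump and sensor, training and weekly calls, so the assigned difference survives. Nor does hypoglycemia at entry show non-response to the feature: the criteria do not record whether it was on, and the background credits suspend pumps with a reduction of up to 30%, not elimination. This part of the reply stands, and it removes any firm power loss.

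It is also fair that stratification cures imbalance, not a smaller effect in some participants; that a covariate cannot simply be added to a rank-sum test; and that three strata in 30 people may leave near-empty cells. These points shape the fix.

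What the reply does not answer is that entry therapy goes unused in both allocation and analysis, and that a prior user's baseline scan would be on treatment. The insulin conflict does depend partly on which insulin injection users take, which is not stated, but the warning about people without pump experience does not.

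**Conclusion.** The point holds as a design weakness of moderate weight. Entry therapy is mixed, control is a different change in each group, and nothing in randomisation or analysis accounts for it. The supportable size is the imbalance: arms differing by 4 or more in about 17% to 25% of allocations, assuming 15/15 allocation and 6 to 10 of 30 sharing an entry therapy. A smaller effect in prior suspend users is plausible, but its size is unknown. The power figures in step 4 are a worst case resting on zero effect in those users and a back-solved control mean, and should not be read as the expected loss. The conflicts in the text stand whatever the power.

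**What to change.** 1. Record insulin therapy and pump mode during the run-in.
2. Stratify randomisation on one two-level factor, for example automated suspend in use at entry (yes/no), or pump against injections.
3. Use the stratified rank-sum (van Elteren) test on that factor for the primary comparison, which keeps the planned rank-based method.
4. Prespecify a sensitivity analysis of participants not using automated suspend at entry.
5. Reconcile Section I, 3.d with the device warnings in Section II, C for injection users. Reconcile the Manual Mode paragraph, including the SmartGuard option, and Appendix 6 with Section I, 3.d on what control participants receive. Which clinical rule applies is for the investigators to decide.

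The cost is one screening field, a slightly more complex list and one extra analysis. The planned 15 per group does not change. Stratifying will not recover a contrast that is smaller in some participants; items 1 and 4 only make it visible.
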